	
(n=10) and women (n=10) to understand the social context of sexual violence in this setting, and focus group discussions (FGDs) with college men (n=12) and university stakeholders (n=12) to elicit feedback on the original program. From these data, we will create scripts in storyboard format of the adapted program. In step 2, we will conduct FGDs with college men (n=12) and university stakeholders (n=12) to elicit feedback on the storyboards and to refine the adapted Program to ensure acceptability. We will use grounded theory to analyze all transcripts inductively and deductively, identifying themes and patterns among themes and comparing the emergent theory with the underlying theory of change of the program. From the final storyboards, we will produce a web-based adaptation of the program in Vietnam. Finally, we will conduct a randomized controlled trial to test the impact of the adapted program (n=200), relative to a health-education control condition (n=200), on knowledge/attitudinal/emotional mediators, and in turn, on sexually violent behaviors, and prosocial bystander behavior in freshmen men attending two universities in Hanoi. Innovation and Long-term Impact. This project will be the first to adapt and to test the impact of a novel, theoretically grounded, web-based intervention to prevent sexual violence perpetration and to promote prosocial bystander behavior among young men for use in a middle-income country. If our project shows that the adapted program is effective cross-culturally, it will have exceptional potential for scale-up to prevent men's perpetration of sexual violence against women globally.

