Survey sample and power. Men 18–24 years and identifying as heterosexual or bisexual and enrolled at HMU and TLU as freshmen on 9/1/2019 are eligible. According to recent enrollment figures, about 890 men matriculate yearly at HMU and TLU. Given a cooperation rate of 67% in similarly focused research among male Atlanta-based undergraduates,⁶⁸ this pool is sufficient to recruit a sample of 400 freshman men for participation in this study.

We computed the required sample sizes to detect our hypothesized effects with a power of .80. We used a Monte Carlo approach⁹¹ to calculate the required sample sizes 1) assuming an attrition rate of 30%; based on 2) Cohen’s medium-to-large-effect-categorization⁹² with regards to the proportion of the variance accounted for, R², by the model (.13 and .26) using corresponding values for a and b;⁹³⁻⁹⁵ and 2) a desired power level of .80. The computer program, Mplus,⁹⁶ was used to complete the computations.

To recruit students, CCIHP personnel will contact department chairs at each university to discuss the study with them. With their agreement, CCIHP will talk with faculty about the study and ask them to announce it in their classes using a flyer with a brief, standard project description. The department chair will obtain email and phone numbers of students. The team has used this strategy successfully to recruit undergraduates. The study staff will utilize student phone numbers to contact students to make sure they check their emails.

Field Methods

Data collection overview. After consent, participants will be assigned randomly, with an equal allocation to Real-Consent or a health-education

control program, using block randomization with random block sizes. Participants and analysts will be blinded to assignments.

Outcomes will be assessed at baseline, posttest (just after finishing the last module), and six months (Table 2). We will consider confounders and modifiers, like social desirability, emotional adjustment, sensation seeking, sexual behavior, aggressive peers, peer and social network diversity, peer social support, witnessing family violence, family cohesion, and social support (Table 2). Questions will model others in the field.⁶⁸

Table 2. Primary (Behavioral) and Secondary (Knowledge/Attitudinal/Emotional) Outcomes at Baseline, Posttest, and Six-Month Follow-Up				
Construct	Scale	Sample item	#	Resp
Primary Outcomes				

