We will test the robustness of the results obtained by investigating potential confounders of paths a and b, which may result in biased estimates. Figure 3 shows how confounders may affect the estimates of relationships between 1) treatment and mediator with tm_1 and tm_2 , and 2) mediator and outcome with mo_1 and mo_2 , which may be biased as a result of omitted or confounding variables.^{117,119} As there will be randomization of the program treatment but not of the mediator variables, most confounders on the treatment-to-mediator relation should be eliminated. Still, we will, perform a balance check on randomization using the control variables listed in Table 5. If imbalance on certain variables is detected, those variables may be controlled for when estimating path a, the program treatment-to-mediator relation. We also will assess the sensitivity of the results to the potential confounders on the mediator-to-outcome relation, path b, using a propensity score approach.^{120,121} The propensity score, or the probability that an individual receives a specified level of the mediator, given a set of observed covariates chosen from Table 5, will be estimated and used as a covariate in the mediation model to estimate path b. The results will be compared to those without any adjustment to detect if possible biases exist due to omitted observed confounders, and if they do, what the directions and magnitude are.

We will perform the intent-to-treat analyses using the software program, Mplus.⁹⁶

Supplemental analyses in the program group. We will conduct several analyses in the program group to assist with the interpretation of findings from the intent-to-treat analyses. First, to gauge possible dose-response relationships between engagement with the program, such as total contact time over the six-session program, and individual post-treatment mediator and outcome variables, we will examine their partial correlations for participants assigned to the program group, adjusting for their corresponding baseline values.¹²² Second, we will assess differential program impact by examining differences in pretest-posttest change scores in mediator and outcome variables across socio-demographic characteristics, such as age, and risk groups, such as alcohol use.

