Analytic issues and strategies. 1) We note and will address relevant analytical issues in this application. Reports of sexual violence. While men may systematically underreport SV perpetration, our own research suggests that men's reported rate of IPV perpetration (37%) can be similar to women's

	
reported rate of IPV exposure (43%) with appropriate quality controls.^{15,123} Our decision to use an online computer-assisted-self-interview platform should enhance disclosure by maximizing the possibility for privacy during the interview. Differential non-participation/attrition. We will explore the differential non-participation/attrition of men to assess for risk of response bias. With the baseline screening, socio-demographic, and other control data, we will model the response probability and use the estimated response probability to compute weights to correct for unit nonresponse using the covariates in Table 5. Estimates on the various outcomes before and after reweighting, and under different assumptions with respect to missing data, will be compared. Item non-response. For covariates with a non-response rate of $\geq 5\%$, we will test for differences between responders and non-responders. We will compare non-responders and responders and may use multiple imputation, assuming the data are missing at random, to fill in the missing values.¹²⁴⁻¹²⁶ Noncompliance. As some participants in the program group may not receive the program, we will estimate complier-average causal effect (CACE) of the program by estimating two latent classes of compliers and non-compliers using engagement of the program as well as covariates and control variables.^{127,128} The CACE results will afford comparisons with and robustness assessment of those of the intent-to-treat analyses, and allow an examination of potential predictive factors of engagement with the program and its intervention implications.¹²⁹ Outliers. We will assess the sensitivity of the results to outliers. We will exclude univariate outliers if their z scores exceed ± 3. Multivariate outliers will be diagnosed using Mahalanobis distance and excluded if $p < .0001$. Results from the complete and reduced data sets will be compared. Convergence issues and improper solutions. We will assess the causes of convergence issues and improper solutions when running the path analyses, such as model misspecification, non-identification, and collinearity—and we will remediate by specifying suitable start values and model re-specifications.¹³⁰ Generalizability. To simplify logistics and enhance feasibility of the RCT, our study sites are two universities. This strategy does not permit generalization to college men in Vietnam, but the two sites enhance the overall diversity of the sample. We will describe our sample clearly to help others understand the young men to whom study findings may be relevant and generalizable.

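### The program-arm dose-response correlations adjust only for the matching baseline score, so self-selected engagement could show a gradient even if the program has no effect

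*Combined protocol and SAP*

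**What the plan says.** The paragraph on supplemental analyses defines the exposure as "engagement with the program, such as total contact time over the six-session program". It relates this to each post-treatment mediator and outcome in men randomised to the program: "we will examine their partial correlations for participants assigned to the program group, adjusting for their corresponding baseline values". It names no further covariate, no comparison with the control arm and no caution about self-selection. The stated purpose of the supplemental analyses is "to assist with the interpretation of findings from the intent-to-treat analyses".

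Three other places deal with confounding or engagement, but none is tied to these correlations:

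- **Intent-to-treat analysis (Plans for analysis).** A propensity score for the mediator is used as a covariate when path b is estimated, because mediators are not randomised.
- **Noncompliance (Analytic issues and strategies).** A CACE analysis models compliers and non-compliers using engagement, covariates and control variables. It is also meant to "allow an examination of potential predictive factors of engagement with the program and its intervention implications".
- **Data collection overview (Field Methods).** A general sentence says that confounders and modifiers will be considered, and lists examples such as social desirability.

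**The concern.** Contact time is not randomised within the program arm. Men who complete more of an online course may differ in ways that also affect how their answers move between baseline and follow-up. Adjusting for the same scale at baseline removes only the part of that difference which the baseline score captures.

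The plan accepts this reasoning for the mediators and applies a propensity score there. It also expects engagement to have predictors. The dose-response correlations nevertheless carry a single adjustment, although alcohol use, sexual behavior, sexual communication and the other baseline scales are all collected.

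The risk is one of interpretation. A positive gradient would be read beside the intent-to-treat result and could be taken as support for it when it reflects only who chose to engage.

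**Working it through.** The plan states no figure for this analysis, so there is none to reproduce. The check asks how large a gradient could arise from a program with no effect.

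**Inputs from the documents**
- Program arm: 200 men (Introduction).
- Attrition: the sample size is computed "assuming an attrition rate of 30"% (Survey sample and power). Retained: 200 × (1 − 0.30) = 140.
- Scales: Table 2 lists 4 primary and 9 secondary, so 13. Over two follow-ups that is up to 26 correlations.

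**Assumptions (not in the documents)**
- Two-sided alpha of 0.05.
- No program effect.
- One unmeasured trait U, independent of the baseline score, correlated k with engagement and k with the part of the follow-up score that baseline does not explain.

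**Induced partial correlation.** Engagement and the residual follow-up score share only U, so partial r = k × k:
- k = 0.2: 0.04
- k = 0.3: 0.09
- k = 0.4: 0.16

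**Chance of a significant result.** By Fisher's z with one covariate, SE = 1/√(140 − 1 − 3) = 1/√136 = 0.0857. Dividing atanh(r) by the SE gives the shift of the test statistic.

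| k | partial r | atanh(r)/SE | significant, Fisher z | significant, simulation (4,000 runs) |
|---|---|---|---|---|
| 0.2 | 0.04 | 0.47 | 7.5% | 8.4% |
| 0.3 | 0.09 | 1.05 | 18% | 19% |
| 0.4 | 0.16 | 1.88 | 47% | 47% |

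With no attrition (n = 200) the simulated rates are 8.3%, 24% and 62%.

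**Across 13 scales at one follow-up.** If U were linked equally to every scale, the expected number of significant results would be 13 × 0.075 = 1.0, 13 × 0.18 = 2.3 and 13 × 0.47 = 6.1. By chance alone it is 13 × 0.05 = 0.65.

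**A second route, with no outside trait.** Suppose engagement depends on a man's true baseline attitude and the scale is measured with error. Adjusting for the measured baseline is then incomplete. At an assumed reliability of 0.8 and engagement–attitude correlations of 0.2, 0.3 and 0.4, the simulated rates are 11%, 19% and 33% (n = 140).

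**Cost of a fuller adjustment.** The 13 baseline scales, age, university and 3 control variables make 18 covariates. SE = 1/√(140 − 18 − 3) = 1/√119 = 0.0917, and 0.0917/0.0857 = 1.07.

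**Cost of requiring a between-arm contrast.** With 140 men per arm, the SE of a difference in z is √2 = 1.41 times larger. For an assumed true partial r of 0.2, atanh(0.2)/0.0857 = 2.36, giving about 66% power in one arm. For the contrast, 2.36/1.41 = 1.67, giving about 39%.

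**The case against.** The strongest reply is that little depends on this analysis. It is labelled supplemental, is meant to gauge possible relationships, and does not enter the tests of H1 to H3. The plan already has a covariate-informed analysis of engagement in CACE, and that is the one assigned to robustness assessment. This stands and limits the severity. It does not remove the point: CACE leaves the correlations as they are, the plan does not say it overrides them, and their stated purpose is to help interpret the main result.

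The illustrated rates also depend wholly on assumed correlations. At 0.2 the excess over 5% is slight. The illustration suits attitude scales better than perpetration outcomes, which may be very sparse; the Background cites a male-reported rate of 0.2%. This stands too.

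A reader might infer three stronger things that the documents do not support:

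- **That the fix would remove the rates shown above.** The simulated trait is unmeasured. Motivation, the obvious candidate, is in neither Table 2 nor the listed confounders, and social desirability is listed but is not a Table 2 control variable. The rates show the possible size of the problem, not the gain from adjusting for collected variables.
- **That the control arm should have served as a negative control.** The posttest is timed to the last module, which may suggest a modular online program in both arms. The documents describe the comparator only as health education and do not say that it is online or that its contact time is logged.
- **That a gradient should be reported only if it exceeds the control-arm gradient.** At the assumed effect above, that rule cuts power from about 66% to 39% and would often hide a real gradient. It also assumes that the same traits drive use of two different programs equally.

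**Conclusion.** The point holds as a minor one. The adjustment set for the dose-response correlations is stated explicitly and is too narrow for a self-selected exposure, and no other part of the plan repairs it. A program with no effect could show a gradient: negligibly often beyond chance if the shared trait correlates 0.2 or less with engagement and with change, and in roughly one test in five or more from 0.3 upward. Those figures rest on 140 retained men, a two-sided 0.05 level, a single trait and equal correlations, all but the first being assumptions. The consequence is confined to how a supplemental result is read; the intent-to-treat tests are not affected.

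**What to change.** Amend the paragraph on supplemental analyses in four ways:

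1. Adjust each dose-response estimate for baseline covariates the trial already has: the Table 2 control variables (alcohol use, sexual behavior, sexual communication), age, university, and the baseline mediator and outcome scores. A propensity-type score for engagement, on the model already planned for path b, would serve equally.
2. Report this beside the estimate adjusted for the matching baseline only.
3. Describe both as associations.
4. State that any causal statement about engagement will rest on the CACE analysis.

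An optional sensitivity check applies only if the control program proves to be online and to log contact time. Run the same model in the control arm as a negative control, with engagement standardised within arm. Do not make the arm-by-engagement test a condition for reporting a gradient.

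The core change needs only analysis wording, with no new participants or survey items. Its price is an interval about 7% wider from 18 covariates at 140 men. Confounding by traits the trial does not measure would remain, which is why the wording as an association matters as much as the covariates.

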Benefits	
Study participants will receive no direct benefit from their involvement in this research. The insights gained from this study, however, should improve college men’s engagement in prevention of sexual violence against women. Considering the extensive protections to be undertaken to minimize potential risks to participants in this research, and the substantial anticipated benefits for future research and policy development, no problems are anticipated that outweigh the advantages of the proposed research.

Compensation	
Each participant will receive graduated payments for completing the baseline, immediate posttest, and six-month follow-up assessments (\$6, \$8, \$10; total \$24). Using only participants’ emails, we will create PayPal accounts (www.PayPal.com) and automatically deposit payments for participants. In

	
other internet-based studies,¹¹³ this payment method has reduced costs and expedited payment versus issuing checks. Several options are available: 1) using only participants' emails, we will create PayPal accounts (www.PayPal.com) and automatically deposit payments for participants; 2) phone card for participants: phone card number will be emailed to participants according to their email submission after completion of each questionnaire; and 3) payment for participants through hosting website of the adapted program through an e-financial solution. In Vietnam, several e-finance platforms are available, but it would depend on the host that we may use.

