
Data Management and monitoring
	
Data systems will be designed to handle the concurrent collection, processing, secure storage, and analysis of project data. New data will be aggregated progressively via a web-based data-entry application (REDCap). Each participant will be assigned a unique number identifying him across waves. The web application will transmit data entered by each participant through an encrypted network connection to a centralized database running on a secure network and infrastructure, ensuring secure electronic data movement. A CCIHP programmer will create, and a CCIHP data manager will run, applications for more refined range/ consistency checks in the centralized database. Systematic data collection errors can be identified, resolved, and documented using a workflow module of the REDCap application. Some statistical software can access data in the central database and store derived variables there. For analyses done with external statistical software, de-identified data will be extracted and held on HIPAA compliant secure networks and computing workstations.

Plans for analysis

[figure not shown]

Descriptive analyses. We will perform univariate analysis of all demographic, screening, mediating, outcome, and control variables for the program and the health-education control groups, individually and combined, to explore distributions, outliers, and missingness. The associations between individual pairs of variables will be examined. Baseline differences on these variables between the program and health-education control condition will be tested. The psychometric properties of the various instruments will be assessed and confirmed.

Intent-to-treat analysis. To assess our aims based on the randomization scheme,¹¹⁴ we will perform mediation analyses via path analysis.^{115,116} Namely, we will assess first whether, relative to men randomized to the health-education control group, men randomized to the program will have improved mediating outcomes (H1). With reference to Figure 2, each of these relationships is represented by path a, or the direct effect of treatment on the mediator. Testing the significance of each path allows us to assess the impact of the program on each mediator. The standardized effect coefficients will serve as effect size measures of the treatment to mediator relations.

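### Differential impact is judged from change in the program arm alone, which cannot separate effect modification from subgroup differences in natural change

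*Combined protocol and SAP*

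**What the plan says.** All references are to the combined protocol and SAP, Quantitative Study Design.

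- **Plans for analysis, Supplemental analyses in the program group.** The opening sentence sets the scope: "We will conduct several analyses in the program group to assist with the interpretation of findings". The second analysis listed is: "we will assess differential program impact by examining differences in pretest-posttest change scores in mediator and outcome variables across socio-demographic characteristics", with age as the example, "and risk groups, such as alcohol use". That sentence does not repeat the restriction to program men, but the heading and the opening sentence govern it, and nothing in the document supports a two-arm reading.
- **Plans for analysis, Intent-to-treat analysis.** H1 is a contrast between arms: "relative to men randomized to the health-education control group, men randomized to the program will have improved mediating outcomes". H2 and H3 build on the same path from assignment to mediator.
- **Field Methods, Data collection overview.** "We will consider confounders and modifiers, like social desirability, emotional adjustment, sensation seeking" and others are named, but no model for a modifier is given.
- **Rest of Plans for analysis.** The path models, confounder checks, attrition weighting, complier analysis and outlier checks contain no assignment-by-characteristic term.
- **Availability of control data.** Under Field Methods, "participants will be assigned randomly, with an equal allocation to Real-Consent or a health-education" control program, and the three assessment times are not split by arm. Compensation points the same way: "Each participant will receive graduated payments for completing the baseline, immediate posttest, and six-month follow-up assessments".

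**The concern.** Differential impact means that the program-control difference varies between kinds of men. The planned contrast asks a different question: whether some program-arm men changed more than others. Men in a risk group such as heavier drinkers may start at a different level, regress towards the mean by a different amount, drift differently, or respond differently to a repeated survey. All of this would be counted as program impact.

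The error can go either way. The analysis can report modification that does not exist, or hide modification that does. It is unbiased only if the subgroups would have changed equally without the program, and program-arm data alone cannot check that.

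The stated purpose of these analyses is to help interpret the intent-to-treat findings. A result carrying the label of differential impact could therefore shape conclusions about whom the program helps, with no randomised comparison behind it.

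**Working it through.** The plan states no sample size, error rate or power for this analysis, so there is no figure to reproduce.

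**Inputs from the document.** 200 men per arm (Introduction), equal allocation (Field Methods), 30% attrition (Survey sample and power): 200 × 0.70 = 140 completers per arm.

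**Assumed inputs.** Two-sided 5% level; a continuous score with SD 1 at both waves; test-retest correlation 0.6; alcohol use split at its median (70 against 70); correlation r of alcohol use with the baseline score of 0.2, 0.3 or 0.5; ratio k of its follow-up correlation to its baseline correlation.

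**Step 1: what each contrast estimates.** For subgroup g, let N_g be the mean change under the control condition and T_g the added program effect.

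- Program arm only: (T1 − T0) + (N1 − N0)
- Control arm only: N1 − N0
- Program minus control: T1 − T0, which is the effect modification

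The planned contrast is the first line. This step needs no numerical assumption.

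**Step 2: false positives with no program effect.** A median split of a normal variable separates the group means by 2 × √(2/π) = 1.596 SD. The subgroups then differ by 1.596r at baseline and 1.596kr at follow-up, so the spurious difference in change is −1.596 × r × (1 − k). At k = 0.6 this is −0.13, −0.19 and −0.32 SD for r = 0.2, 0.3 and 0.5. The SD of change is √(2 − 2 × 0.6) = 0.894, and the standard error is 0.894 × √(1/70 + 1/70) = 0.151. For r = 0.3 and k = 0.6, z = 0.19/0.151 = 1.27, which gives rejection in about 24% of trials. Simulation (20,000 trials per cell, Welch t-test) gives:

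| k | r = 0.2 | r = 0.3 | r = 0.5 |
|---|---|---|---|
| 0.6 | 13.1% | 23.8% | 56.6% |
| 0.8 | 7.1% | 9.9% | 18.1% |
| 0.9 | 5.8% | 6.1% | 8.5% |
| 1.0 | 4.9% | 5.1% | 4.9% |

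**Step 3: masking.** Suppose true modification is −0.4 SD and the natural difference is 0, +0.2 or +0.4 SD. The net contrast is −0.4, −0.2 or 0, so |z| = 2.65, 1.32 or 0. Simulated detection is 75.0%, 25.7% and 5.0%.

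**Step 4: more participants do not help.** With differences now in units of the SD of change and no true modification, a natural difference of 0.2 is declared significant in 22% of trials with 140 completers and 29% with 200. A difference of 0.4 gives 66% and 81%.

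**Step 5: the two-arm interaction.** With 140 per arm and adjustment for baseline, the residual SD is √(1 − 0.6²) = 0.8, and the standard error over four cells of 70 is 0.8 × √(4/70) = 0.191. Simulated false positives are 4.6% to 5.3% over the nine combinations of k = 0.6, 0.8, 1.0 and r = 0.2, 0.3, 0.5. The interaction detectable with 80% power is 2.80 × 0.191 = 0.54 SD. It ranges from 0.48 SD (test-retest 0.7, 50/50 split) to 0.63 SD (test-retest 0.5, 30/70 split). Simulated power is 33% at 0.3 SD, 55% at 0.4 SD and 74% at 0.5 SD.

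**The case against.** The strongest reply is about weight. The section heading tells the reader that the analysis is supplemental and confined to the program group, it is kept apart from the intent-to-treat analysis, and no primary test depends on it. That stands: a careful reader is warned, and misreading is a risk rather than a certainty.

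The largest percentages also come from an unfavourable case. With k = 0.6 and test-retest 0.6, alcohol use relates to follow-up only through the baseline score. If it tracks the stable part of the score, k is 1.0 and the error rate is nominal. Nothing in the document favours one value over another, so the whole table should be read, not its first row.

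The interval is short. A seven-month study with follow-ups at 0 and 6 months leaves about one month from baseline to posttest, so large natural drift is less plausible. Regression to the mean and repeat-survey effects, however, do not need a long interval.

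Finally, the figures are for continuous scales. Sexual and partner violence are listed as primary outcomes, and the Background cites a reported perpetration rate of 0.2% among men. SD-based error rates and detectable differences do not carry over to rare or skewed outcomes. Age was not simulated.

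None of this answers Step 1. The planned contrast still estimates a different quantity from the one it is named for.

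**Conclusion.** The concern holds. The only analysis specified for differential impact omits the control arm and so mixes effect modification with subgroup differences in natural change. That conclusion follows from the text and from Step 1.

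The size is conditional. For continuous scores, 140 program completers and test-retest 0.6, the false-positive rate runs from 5% to 57% over the range examined. Power to detect a true 0.4 SD modification falls from 75% to 26% or 5% when natural change differs by 0.2 or 0.4 SD in the opposite direction. The subgroup correlations and natural differences are assumptions.

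The tests of H1-H3 are untouched. This should be corrected because the analysis is meant to guide their interpretation, but it does not threaten the trial's main conclusions.

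**What to change.** Replace the one-arm rule with assignment-by-characteristic interactions in all randomised men, with the follow-up score as outcome and its baseline value as covariate. Report the program-control difference with its confidence interval at each level of the characteristic. Name a short list of modifiers in advance, because four primary and nine secondary measures crossed with an open list would produce many tests. Label the results exploratory. For the violence outcomes, put the same interaction in a model suited to rare or skewed data.

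Change within the program arm may stay as description, provided it is not called differential impact.

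The change costs SAP wording only, since control men are surveyed at the same waves. The real downside is precision: about 0.54 SD is detectable with 80% power, and power is 33% at 0.3 SD. The SAP should say so, and should say that a non-significant interaction is not evidence of equal impact.
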